7 STUDY DESIGN

7.1 Point or limit points

Criteria for the evaluation.

Efficacy measurements:

Main efficacy criterion

Efficacy will be determined by taking cultures of the lower conjunctival cul-de-sac background quantifying (colony-forming units) and identifying genus and basal and final microbial species.

It will be determined as effective if there is a reduction in the number or species of bacterial flora comparing the basal culture against the end between the five different groups of patients and / or if there is a reduction or absence of the following specific signs and symptoms: burning, tearing, Foreign body sensation, pruritus, photophobia, conjunctival hyperemia, chemosis, palpebral edema and secretion, membranes and / or pseudomembranes when comparing the study medication versus Moxifloxacin and versus Gatifloxacin from baseline to final visit.

Efficiency parameters

- The effectiveness of the drug will be evaluated by means of:

1. Clinical referral

2. Microbiological remission

Clinical remission will be evaluated by means of the signs and symptoms that the patient presents at the beginning and at the end of the study.

Variable	Operationalization	Measurement scale	Value
Secretion	Dependent Qualitative ordinal	Absent Present	Must be recorded as absent in 95% of the subjects evaluated
Conjunctival hyperemia	Dependent Qualitative ordinal	Absent Mild Moderate Severe	You must comply with the following: • Absent \geq 95.0% • Mild \leq 5.0% • Moderate \leq 2.5% Severe \leq 1.0%
Chemosis	Dependent Qualitative ordinal	Absent Present	Must be recorded as absent in 95% of the subjects evaluated
Eyelid edema	Dependent Qualitative ordinal	Absent Present	Must be recorded as absent in 95% of the subjects evaluated
Corneal epithelial defects	Dependent Qualitative ordinal	Affected area, percentage	Percentage of affected area less than 95%

The microbiological remission will be evaluated by means of the culture taken from the conjunctival sac fundus.

Variable	Operationalization	Measurement scale	Value
Culture	Dependent Discrete quantitative	UFC * / ml Eradication Reduction Proliferation	Must be recorded as absent in 95% of the subjects evaluated

* Colony forming units

The drugs under study will be considered effective if the patient has any of the following:

1. Clinical remission + Microbiological remission.
2. Clinical referral.
3. Microbiological remission.

Security measurements:

Adverse events and visual capacity.

Evaluation parameters

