The central laboratory in charge of the processing of the samples will be asked for Gram stain and special attention to the growth in the culture of the following bacteria:

Staphylococcus aureus, Staphylococcus albus, Pseudomonas aeruginosa, Streptococcus pneumoniae, Haemophilus influenzae, Streptococcus pyogenes, Klebsiella pneumoniae Escherichia coli, Neisseria gonorrhoeae, Streptococcus viridans, Moraxella catarrhalis.

The technique for collecting the sample will be done using a swab. These techniques are not limiting, and it is up to the doctor to select one of them according to the case.

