Cuadro 1. Eficacia de medicamentos para erradicación de bacterias en infecciones oculares (Conjuntivitis) reportada en publicaciones.

Tratamiento	Eficacia Absoluta	Total ojos		Eficacia %
		n	n	
MOXI-AF¹		424	316	74.53%
Placebo (Vehículo)¹		423	237	56.03%
Zymar²		52	40	76.92%
Placebo (Vehículo)²		48	28	58.33%
Zymaxid²		333	193	57.96%
Placebo (Vehículo)²		325	148	45.54%

Tratamiento	Eficacia específica por bacteria			
MOXI-AF¹	Haemophilus influenzae	67	66	98.51%
	Streptococcus pneumoniae	22	19	86.36%
	Staphylococcus aureous	17	16	94.12%
Placebo (Vehículo)¹	Haemophilus influenzae	52	31	59.62%
	Streptococcus pneumoniae	18	9	50.00%
	Staphylococcus aureous	15	12	80.00%
Zymar²	*	52	48	92.31%
Placebo (Vehículo)²	*	48	34	70.83%
Zymaxid²	*	333	301	90.39%
Placebo (Vehículo)²	*	325	228	70.15%

* **Nota:** La eficacia específica por bacteria en los estudios con Zymar y con Zymaxid no se presenta para cada bacteria sino para la totalidad de bacterias que aparecieron en el cultivo inicial y ya no aparecieron en el cultivo post-tratamiento.

¹ Microbiological Efficacy of a New Ophthalmic Formulation of Moxifloxacin Dosed Twice-Daily for Bacterial Conjunctivitis. Shachar Tauber et.al. En Adv Ther. (2010) 28(7):566-574.

² Clinical use of gatifloxacin ophthalmic solution for treatment of bacterial conjunctivitis.

Lorenzo J. Cervantes y Francis S. Mah. En Clinical Ophthalmology. 2011:5 495-502.

To calculate the sample size, we obtained the overall average of absolute efficacy for patients treated with some medication and for patients treated with placebo. For patients treated with medication, the absolute efficacy (total disappearance of bacteria in the post-treatment culture) was 69.8% and for those treated with placebo it was 53.3%. The specific efficacy (disappearance of a specific bacterium that was present in the pre-treatment culture) for the groups treated with some medication was 92.34% and for patients treated with placebo 66.12%.

With these figures, we can calculate the sample size needed to detect that level of differences reported between patients with bacterial conjunctivitis treated with medication vs. patients treated with placebo.

Annex 1 develops the calculations for the sample size necessary to detect the differences in the percentage of efficacy to eliminate bacteria from patients with bacterial

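### Section 7.1 counts any fall in bacterial number or species as effective, yet its culture row asks for absence and leaves its three classes undefined, so persistent or replaced growth can be read as success

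*Combined protocol and SAP*

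**What the plan says.** **Data collected.** Section 7.1 has cultures taken at baseline and at the end, "quantifying (colony-forming units) and identifying genus and basal and final microbial species".

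**Main criterion (7.1).** "It will be determined as effective if there is a reduction in the number or species of bacterial flora", and/or if signs and symptoms lessen or disappear. No minimum reduction is given, and there is no rule for a new species.

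**Culture row of the microbiological remission table (7.1).** The scale is "UFC * / ml Eradication Reduction Proliferation". The target is "Must be recorded as absent in 95% of the subjects evaluated". The classes are not defined, and the row does not say which of them are remission.

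**Success per patient (7.1).** "The drugs under study will be considered effective if the patient has any of the following": clinical and microbiological remission together, clinical alone, or microbiological alone.

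**Section 23.** Two efficacy definitions are used for sizing. Absolute efficacy means that no bacteria remain in the post-treatment culture. Specific efficacy is the "disappearance of a specific bacterium that was present in the pre-treatment culture". The plan does not say which one the trial endpoint follows.

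**Sampling (section 17).** The swab procedure is described as general, with the exact one to come from the central laboratory. The sub-section then ends: "These techniques are not limiting, and it is up to the doctor to select one of them according to the case".

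**Aim (section 6.1).** Non-inferiority to moxifloxacin and gatifloxacin. No margin is given in the documents.

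**The concern.** Two statements in one section set different bars. Under the main criterion a lower count is enough. Under the culture row only an absent culture meets the target. The three classes do not settle the matter, because they are undefined and leave out two ordinary outcomes: the same organism at much the same count, and a different organism at the final visit.

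Two separate swabs will seldom give identical counts, so a persistent infection will usually show either a rise or a fall. With no minimum reduction, the falls satisfy the main criterion. If such eyes are counted as responders at similar rates in every arm, the arms are drawn together. In a trial that aims to show non-inferiority, that error works in favour of the sponsor's hypothesis.

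**Working it through.** **1. Outcomes set against the rules of the plan**

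| Final culture | Main criterion (any reduction) | Culture row (absent) | Class available |
|---|---|---|---|
| No growth | success | success | Eradication |
| Baseline organism, count slightly lower | success | failure | Reduction |
| Baseline organism, count equal | failure | failure | none |
| Baseline organism, count higher | failure on count | failure | Proliferation |
| Different organism, count lower | success | failure | Eradication (by species) or Reduction |
| Different organism, count equal or higher | depends on how loss of a species is read | failure | unclear |

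The two rules disagree in the second and fifth rows and may disagree in the sixth. If there is no true change and swab error is symmetric, about half of the counts will fall by chance, ignoring ties. The documents do not give the share of eyes with no true change.

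**2. The plan's own sample sizes under the two definitions**

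Inputs (section 23 and Annex 1): 69.8% v 53.3% absolute, 92.34% v 66.12% specific; two-sided alpha 0.05, power 80%, 1:1, Fleiss formula with continuity correction, m = 0.25 m' [1 + √(1 + 4/(m' |P2 − P1|))]².

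- Absolute: m' = 135.272 and |P2 − P1| = 0.165 give m = 147.1. The plan states 147; rounding up gives 148.
- Specific: m' = 36.373 and |P2 − P1| = 0.2622 give m = 43.7. The plan states 44.

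Both figures reproduce. The choice between the two definitions moves the size from 147 to 44 per group.

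**3. How far the definitions differ in the literature table (section 23, Cuadro 1)**

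These are the studies that report both measures on one denominator.

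| Group | Specific − absolute | Gap |
|---|---|---|
| Zymar | (48 − 40)/52 | 15.4% |
| Its vehicle | (34 − 28)/48 | 12.5% |
| Zymaxid | (301 − 193)/333 | 32.4% |
| Its vehicle | (228 − 148)/325 | 24.6% |

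Under the stated definitions, the gap is the share whose baseline bacteria were gone but whose culture was not clear. It assumes that both counts come from the same eyes. Treatment in those studies lasted three days; here it lasts seven, with the final culture on day 8.

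**4. Direction of the bias (illustration; f is assumed)**

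If a fraction f of non-eradicated eyes counts as success in both groups, the difference becomes (1 − f)(P1 − P2). Starting from the plan's 16.5 points:

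- f = 25%: 0.75 × 16.5 = 12.4 points
- f = 50%: 0.50 × 16.5 = 8.2 points (8.25 before rounding)
- f = 75%: 0.25 × 16.5 = 4.1 points

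This shows the mechanism on a drug–placebo contrast. It is not an estimate for this trial, which has no placebo arm.

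**5. Why a fixed minimum fall cannot be taken from the documents**

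With no true change, the chance of a fall of at least 1 log10 is 1 − Φ(1/(SD√2)). For assumed single-swab SDs of 0.3, 0.5 and 0.7 log10 this is 0.9%, 7.9% and 15.6%. The documents give no SD, so any bound has to come from the laboratory's own repeatability data.

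**The case against.** **The plan does not code these eyes as successes.** A reader might infer that every persistent or replaced infection is forced into a success class. The text does not support that. An equal count is not a reduction, a replacement at a higher count is not a fall in number, the target value asks for absence, and Proliferation is available as a non-success class. If the target value governs, every non-eradicated eye fails and no dilution arises. This objection stands against the strong reading. It does not remove the problem, because the main criterion is also written down, a small fall meets it literally, and nothing gives one rule precedence.

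**The 15% and 32% are not unclassifiable eyes.** This is correct. They are arm-level subtractions from three-day studies, many such eyes could be coded as Reduction, and the vehicle groups show 12.5% and 24.6%. The drug-minus-vehicle gaps are only about 3 and 8 points.

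**Other growth need not be infection.** Section 4.1 (Justification) notes that some of these organisms normally live on the conjunctiva. That is a good reason for a sensitivity analysis, but it does not justify leaving the class undefined.

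**Sampling is partly covered.** The central laboratory is to describe the procedure, and a swab is specified. The documents do not show that baseline and final samples are taken differently. They do contain a sentence that allows it.

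**Limited reach.** Clinical remission alone is enough for success, so the culture class changes the outcome only for patients without clinical remission. That is true, and it limits the effect.

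**Conclusion.** The point holds as a contradiction and a gap in the endpoint definition. Section 7.1 sets an any-reduction rule beside an absence target, with classes that are neither defined nor exhaustive. Followed as written, the main criterion makes a success of a persistent infection with a trivial fall in count. A replaced organism can go either way, and section 23 offers an opposed definition for each answer. Because microbiological remission alone suffices, the coding can decide a patient's result. The expected direction, if miscoding is similar across arms, is towards no difference.

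The size in this trial cannot be computed. The documents give no swab repeatability, no share of persistent or replaced cultures, and no non-inferiority margin. The literature gaps and the shift from 147 to 44 per group show only that the choice of definition is consequential.

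This should be settled before unmasking. Counts, genus and species are already recorded at both visits, so it can be.

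**What to change.** Before unmasking, state in section 7.1 and the analysis plan:

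1. **Population.** The microbiological endpoint is assessed in eyes with growth at baseline. Sections 15.1 and 18.2 start treatment on clinical suspicion, before culture results, so an eye negative at both visits would otherwise pass as eradicated.
2. **Remission.** Microbiological remission is eradication: no growth at the final culture. This agrees with the row's target value and with absolute efficacy.
3. **Non-remission.** Reduction without eradication, persistence and proliferation, each defined on count and species.
4. **Baseline species cleared with other growth.** Its own class: non-remission in the main analysis, remission in a sensitivity analysis that follows specific efficacy.
5. **Reduction.** Reported as secondary, with any minimum fall set by the central laboratory from swab repeatability.
6. **Main criterion.** Reworded to match.
7. **Sampling.** In section 17, remove the doctor's choice of technique and require the central laboratory's procedure, the same at both visits.

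**Cost.** Form coding, a laboratory manual line and analysis plan wording; no extra samples. The stated microbiological response rate will be lower, and eyes without baseline growth leave this endpoint; the documents do not say how many. Eradication also corresponds to the plan's 147 per group rather than its 44, against 60 eyes planned, although both figures were derived for a drug–placebo difference and not for non-inferiority.

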The pathogenesis usually involves the disruption of the ocular surface defense mechanisms, due to trauma, tear film dysfunction or palpebral abnormalities, etc.

Usually its installation occurs 1 to 2 days after contact, characterized by rapid appearance of clinical signs such as palpebral edema, hyperemia, mucopurulent secretion, membranes and / or pseudomembranes.

The main infectious agents in adults are *H. influenzae*, staphylococci and streptococci. *H. influenzae*, *S pneumoniae*, and *Moraxella catarrhalis* are the most frequent agents in children. The course of the clinical picture is 7 to 10 days long.

Due to its clinical presentation, it is convenient to divide them according to their installation time, in acute, acute or chronic hyperinflation, and can guide diagnostic tests and empirical treatment according to the time of presentation.

Common pathogens according to the time of evolution

Acute	Híper Acute	Chronic
Staphilococcus Aureus.	Neisseria Gonorreae.	Moraxella catarrhalis.
Streptococcus pneumoniae.	Neisseria meningitidis.	Moraxella Lacunata.
Haemophilus influenzae.		Enterobacterias.

Special conditions:

In sexually active subjects who do not give up the clinical picture with empirical treatment (ceftriaxone 1gr b.i.d), we should investigate *Chlamydia Trachomatis* and add the relevant treatment.

In the case of infants or minors (less than 2 years old), we should consider granting systemic treatment because 50% of them concur with infections in other systems.

In oculo-vaginal infections we must investigate on strains compatible with trachoma (A-C); since we must remember that it affects more than 40 million subjects in areas of poor hygiene and continues to be a leading cause in non-reversible blindness.

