In other regions, such as India (with characteristics probably similar to our environment) it is observed that *S. Aureus* frequently causes infections of the eyelids and conjunctiva, *S. pneumoniae* is responsible for those inherent to the lacrimal apparatus and *S. coagulase negative* corresponds to infections intraocular.

In 10-year reviews in developed countries (eastern US) 1997- 2008, a tendency is observed in turn to the prevalence of *Staphylococcus Aureus* as the main ocular pathogen.

The effectiveness of 4th generation quinolones in the treatment of bacterial conjunctivitis since 1 year of age with a posology that varies from 2 to 4 times a day has been demonstrated in recent evidence, which corresponds to the preclinical studies and phase I of the drug. viii

We can also state the following points that support its use in infants and children under 18 years.

Due to the satisfactory results of the phase I study of the medication carried out in the adult population, in a phase II its implementation is justified in the child population since the evidence collected in said study allows inferring that its use is safe and effective to use it in the model of proposed disease, bacterial conjunctivitis. ix

Also the incidence of adverse events of musculoskeletal toxicity in children with chronic use of quinolones of 4th generation is reported as not significant at 5-year follow-up, so it was concluded that its use is adequate in this population. viii, ix

Currently, up to 26% resistance to the 4th generation quinolones (moxifloxacin, gatifloxacin and levofloxacin) is reported in strains of methicillin-resistant *Staphylococcus epidermidis*, so pazufloxacin represents a treatment option in such cases. ix, x

Sophia S.A de C.V. has developed a new ocular topical formulation belonging to the group of the fourth-generation quinolones, called Pazufloxacin mesylate, which has shown through in vivo and in vitro studies to have greater antimicrobial activity against methicillin-resistant *S. aureus*, *Haemophilus influenzae* ampicillin resistant, as well as *E. coli*, *Proteus mirabilis*, *Serratia marcescens* and *P. aeruginosa*. It should be noted that this formulation is free of preservatives.

Initially indicated for all those patients with bacterial conjunctivitis to susceptible organisms.

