5 CLINICAL STUDIES

A phase I clinical study was conducted to evaluate the safety and tolerability of the PRO157 ophthalmic solution in healthy volunteers. The tolerability was determined by the presence of: burning, hyperemia, chemosis, foreign body sensation and lacrimation. Safety by assessing visual acuity and / or visual capacity, fluorescein staining, green lysine and intraocular pressure and the frequency of adverse events. A total of 5 visits were made.

- Visit 0: Basal, day 0 (selection period).
- Visit 1: Follow-up, day 2 (treatment period).
- Visit 2: Follow-up, day 4 (treatment period).
- Visit 3: Follow-up, day 7 (treatment period).
- Visit 4: Final day 11 (final visit).

During which time the drop was applied 4 times a day in both eyes, the results that were obtained determined that the variables that reflect tolerability of the product, such as ocular burning, red eye, conjunctival hyperemia and lacrimation, remained predominantly in a low intensity (mild). There was no presence of chemosis or secretion. More than 88% of the eyes studied showed no sensation of a foreign body in the eye and more than 70% of the eyes did not present pruritus in the different evaluations. Variables that reflect the safety of the product, such as visual capacity and intraocular pressure, were always within normal parameters. No findings were reported during the revision of the anterior segment or the posterior segment, none of the eyes studied showed any degree of fluorescein or green lysine uptake in the corneal surface, there were no reports of adverse events. Vi

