• The safety of the use of PRO-157 will be evaluated in the visits indicated in the schedule, through the following parameters:

1. Visual capacity
2. Eye surface
3. Exploration of the previous segment
4. Exploration of the posterior segment
5. Burning
6. Foreign body sensation
7. Lachrymation
8. Conjunctival hyperemia
9. Itching
10. Photophobia
11. Chemosis
12. Tear discharge
13. Eyelid edema
14. Membranes / pseudomembranes
15. Scales
16. Corneal epithelial defects
17. Adverse events

It will be considered that the drug under evaluation is safe for use in humans if there are no changes in the parameters indicated in more than 5% of the subjects, in both eyes, if the

patient goes to all the visits of the study and complies with adherence to treatment $\geq 80\%$ during the time of evaluation of the study.

Variable	Operationalization	Measurement scale	Value
Visual ability	Independent Discrete quantitative	Points logMAR 0-1 0 = Snellen 20/20	Do not present change in 1 line in the Snellen letter or in 1 logarithmic point (log MAR)
Ocular surface	Dependent Qualitative ordinal	Absent Present	Abnormalities in any area of the ocular Surface
Exploration of the previous segment	Dependent Qualitative ordinal	Normal Abnormal	Abnormalities in any of the structures included: cornea, iris, pupil, irido-corneal and crystalline angle.
Exploration of the posterior segment	Dependent Qualitative ordinal	Normal Abnormal	Abnormalities in any of the structures included: vitreous, retina, macula and the optic nerve
burning	Dependent Qualitative ordinal	Absent Present	Must be recorded as absent in 95% of the subjects evaluated
strange body sensation	Dependent Qualitative ordinal	Absent Present	Must be recorded as absent in 95% of the subjects evaluated
tearing	Dependent Qualitative ordinal	Absent Present	Must be recorded as absent in 95% of the subjects evaluated

Secretion	Dependent Qualitative ordinal	Absent Present	Must be recorded as absent in 95% of the subjects evaluated
Conjunctival hyperemia	Dependent Qualitative ordinal	Absent Mild Moderate Severe	You must comply with the following: Absent ≥ 95.0% Mild ≤ 5.0% Moderate ≤ 2.5% Severe ≤ 1.0%
Photophobia	Dependent Qualitative ordinal	Absent Mild Moderate Severe	You must comply with the following: Absent ≥ 95.0% Mild ≤ 5.0% Moderate ≤ 2.5% Severe ≤ 1.0%
Chemosis	Dependent Qualitative ordinal	Absent Present	Must be recorded as absent in 95% of the subjects evaluated

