Eyelid edema	Dependent Qualitative ordinal	Absent Present	Must be recorded as absent in 95% of the subjects evaluated
Membranas Pseudomembranes	Dependent Qualitative ordinal	Absent Present	Must be recorded as absent in 95% of the subjects evaluated
Scales	Dependent Qualitative ordinal	Absent Present	Must be recorded as absent in 95% of the subjects evaluated

Epithelial defects corneal	Dependent Qualitative ordinal	Affected area, percentage	Percentage of the affected area 95%
Adverse events	Dependent Qualitative ordinal	serious Not Serious	Must be recorded as absent in 95% of the subjects evaluated

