- Any complication or lack of control that the doctor considers should be treated differently.

- **Elimination Criteria**

- Clinicians:

a. Any complication or lack of control that the doctor considers should be treated differently. The following points should be considered:

i. The no improvement of the initial clinical signs and symptoms.

ii. Diagnosis added or different to that of acute bacterial conjunctivitis.

iii. Use other medications outside the study.

b. * It is reiterated that they are minimum parameters to be considered, any other case in which the investigator considers necessary the elimination of the patient and suspension of the treatment must be informed and evaluated by the sponsor.

- For the sponsor:

- a. By its will, it will not have penalties, nor will it lose benefits to those that it already has right.
- b. For the total term of the scheduled visits in the clinical study.
- c. For a serious adverse event related to the medication that endangers your health.
- d. Why the medication does not work at the doctor's discretion.

and. Why, by sponsor's decision, the study ends earlier.

In case of withdrawal for any of these reasons or any other at the discretion of your doctor, you will be prescribed again the medication of which you were already a user or any other that is of benefit for your best treatment.

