20.1 Events to be registered

An adverse event is defined as any unfavorable medical occurrence in a subject that is participating in a clinical trial, whether or not there is a causal relationship with the study drug and / or experimental procedures, that is present or detected as of the date that the patient signs the form of information and consent, regardless of the period of the study.

Therefore, the investigator will document as an adverse event:

- Any unfavorable and unintended sign, including an abnormal finding of an additional examination that the investigator considers clinically important,
- Any intercurrent symptoms or illness,
- Any worsening during the study of a symptom or disease already present when the patient entered the study (increase in frequency and / or intensity), and which:
 - It is detected during a study visit or in an additional examination,
 - Be present from the previous visit of the study and notify the patient.

A serious adverse event, that is, an event that, regardless of the dose of the study drug administered:

- How the patient's death results
- Be a threat to life,

Note: the term "threat to life" refers to an event in which the patient was at risk of death at the time of the event; it does not refer to an event that hypothetically could have caused death if it had been more serious.

- How persistent or important disability / disability results. Note: an event that seriously disrupts the patient's ability to lead a normal life, in other words that causes a significant change, deterioration, injury or alteration of the functions or body structure of the patient, physical activity and / or quality of life.
- Be a congenital anomaly / birth defect. Exposure to the study drug before conception (in man or woman) or during pregnancy that causes an adverse outcome in the child.

Note: any event that may not be an immediate threat to life or result in death or hospitalization but may endanger the patient or may require intervention to avoid one of these outcomes (eg, edema or allergic bronchospasm requiring treatment) intensive at home, blood dyscrasia, seizures that do not cause hospitalization, or development of drug dependence or drug abuse).

Consumption of the study drug by a person other than the patient:

- Minors: any consumption of the study drug with or without medical consequences must be notified immediately to the sponsor.

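### Section 7.1's numerical safety threshold is wrong as written: it gives no direction of change, reuses remission limits as safety limits, covers only adherent completers, and mismatches the vision units

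*Combined protocol and SAP*

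**What the plan says.** All references are to the combined protocol and SAP.

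- **The rule.** Section 7.1 lists 17 safety parameters and calls the drug "safe for use in humans if there are no changes in the parameters indicated in more than 5% of the subjects, in both eyes". The same sentence requires the patient to attend all study visits with adherence of at least 80%. The parameters "will be evaluated in the visits indicated in the schedule".
- **The table beneath it.** Most sign and symptom rows carry the value "Must be recorded as absent in 95% of the subjects evaluated". Hyperemia and photophobia have graded limits: absent in at least 95%, with caps on mild, moderate and severe. The clinical remission table earlier in Section 7.1 sets the same limits for secretion, conjunctival hyperemia, chemosis and eyelid edema.
- **Vision row.** The limit is a change of one Snellen line or of one logMAR point, with no direction. Section 17 (Visual acuity) sets one line at 0.10 logMAR and 20/200 at 1.0.
- **Population.** Section 15.3 keeps the data of withdrawn patients for an intention-to-treat safety analysis. Section 23 (Analyzed data set) defines that population as everyone with at least one dose.
- **Adverse events.** Section 20.1 counts "Any worsening during the study of a symptom or disease already present when the patient entered the study".

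**The concern.** Patients enter with the disease whose signs are on the safety list, so most of the change expected in those signs is improvement. A limit on change needs a direction, and this one has none. The table then sets a different test, near-complete absence of the sign. That measures cure, and for four signs it is the remission limit itself. A harmless but only partly effective regimen would fail on safety for a reason that belongs under efficacy.

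The attendance and adherence condition removes early stoppers from the threshold. The elimination criteria in Section 15.2 include complications, "The no improvement of the initial clinical signs and symptoms" and related serious adverse events, so those removed may be the patients who matter most for safety. Visual capacity is one of the two safety criteria named in Section 18.1, and its limit is given in two units that differ tenfold. At stake is whether the threshold statement means the same thing to everyone who applies it, and whether the reading is fixed before the data are seen.

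**Working it through.** **Inputs.** The 5% and 95% limits are from Section 7.1, and 60 eyes per group is from the Summary and Section 8. The number of subjects is not stated: 60 study eyes come from 60 subjects if each has one infected eye and from 30 if each has two, so both are shown. The number of subjects allowed over the limit is t = floor(0.05n): 3 of 60 or 1 of 30. Persistence and baseline prevalence are not in the documents and are assumed over a range. Subjects are treated as independent.

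**1. The plan's own figure.** With logMAR = log10(denominator/20), the Snellen values in Section 17 give 20/25 = 0.097, 20/40 = 0.301, 20/100 = 0.699 and 20/200 = 1.000. The 0.10 per line reproduces. One logMAR is 1.0/0.10 = 10 lines, so the two limits in the vision row differ tenfold.

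**2. Persistence scored as a safety failure.** Suppose nobody worsens and a sign persists in a proportion q. The row is met if at most t subjects still have it, with X binomial(n, q).

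| q (assumed) | P(X ≤ 3), n = 60 | P(X ≤ 1), n = 30 |
|---|---|---|
| 5% | 0.65 | 0.55 |
| 10% | 0.14 | 0.18 |
| 15% | 0.015 | 0.048 |
| 20% | 0.001 | 0.011 |

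For n = 30 and q = 0.10: 0.9^30 + 30 × 0.1 × 0.9^29 = 0.042 + 0.141 = 0.184. For hyperemia these are upper bounds, because the caps on moderate (2.5%) and severe (1%) must also be met.

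**3. If improvement also counted as change.** Let b subjects have the sign at baseline, r resolve and w develop it.

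- Table: b − r + w ≤ t.
- Sentence: r + w ≤ t.
- Adding the two: b + 2w ≤ 2t, so b ≤ 2t.

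Both can be met only if the sign is present at baseline in at most 6 of 60 (10%) or 2 of 30 (6.7%). At an assumed 50% prevalence, at least 30 − 3 = 27 of 60 must resolve to meet the table, against 3 changes allowed by the sentence. If only worsening counts, this conflict disappears but the result in step 2 does not.

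**4. Population.** Suppose the only subjects who worsen are those who stop early (constructed example, exact 95% CIs).

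| Subjects per arm | Early stoppers, all worsened | Adherent completers | All dosed |
|---|---|---|---|
| 60 | 4 | 0/56 = 0% (0 to 6.4%) | 4/60 = 6.7% (1.8 to 16.2%) |
| 30 | 2 | 0/28 = 0% (0 to 12.3%) | 2/30 = 6.7% (0.8 to 22.1%) |

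The completer figure meets the 5% limit and the all-dosed figure does not.

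**The case against.** The strongest reply is that worsening is plainly what was meant. Section 20.1 defines adverse events that way, and Section 15.2 treats lack of improvement as a reason for elimination. This stands as the more natural reading, so step 3 is conditional. A reader might infer that the rule would condemn a curative drug, but that follows only on the less natural reading. The text still does not state a direction, and step 2 holds on either reading.

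Other stronger readings that the documents do not support:

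- **That this is the plan's only route to a safety conclusion.** Section 6.1 frames safety as part of a non-inferiority hypothesis, and Sections 6.2, 7.1 and 18.1 name adverse events and visual capacity.
- **That every symptom row repeats a remission limit.** The remission table has no row for burning, foreign body sensation, tearing, photophobia, membranes or scales. Burning and foreign body sensation were tolerability measures in phase I (Section 5) and have a place in a safety table.
- **That phase I shows the 95% bar to be out of reach.** The phrase "More than 88% of the eyes studied showed no sensation of a foreign body in the eye" gives a floor, counted in eyes. It does not show a rate below 95%.
- **That worsening in one eye goes uncounted.** Section 8 applies drops and procedures to both eyes, so the reference to both eyes more naturally means that both are assessed.
- **That early stoppers' safety data are lost.** Sections 15.3 and 23 keep them. The defect is that the threshold leaves them out.

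It is also fair to say that the 4-of-60 case is constructed and both its intervals include 5%, and that if both vision limits apply, one line is reached first, so the mismatch is a unit slip. Loose translation may explain some phrasing, but not the explicit limits, the attendance condition or the logMAR figure.

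**Conclusion.** The numerical safety threshold in Section 7.1 is wrong as written, in three respects.

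- **Direction and purpose.** No direction is given, and four signs carry remission limits as safety limits. With no worsening and 10% persistence, such a limit is met with probability 0.14 (60 subjects) or 0.18 (30). This rests on assumed persistence and independent subjects. The stricter bound of 6 of 60 or 2 of 30 at baseline applies only if improvement counts as change.
- **Population.** The rule covers adherent completers, against the all-dosed safety population of Sections 15.3 and 23. In the illustration, four early stoppers of 60, or two of 30, decide whether the limit is met.
- **Units.** One Snellen line and 1 logMAR differ tenfold under Section 17's own definition, and the passages must be reconciled.

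Adverse events are still recorded and described for everyone. The fault lies in the threshold statement, which should be corrected before the data are analysed.

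**What to change.** 1. State that the 5% limit applies to the proportion of subjects in whom a listed parameter worsens from baseline or newly appears, in either eye, at any post-baseline assessment. Include unscheduled and discontinuation visits and, for adverse events, the day 23 call. Count subjects, not eyes.
2. Compute it in all subjects with at least one dose, report it per arm with an exact 95% CI, and delete the attendance and adherence condition from the rule.
3. In the safety table, replace the 95% absence values and the graded hyperemia and photophobia limits for disease signs and symptoms with this worsening or new-onset measure. Burning and foreign body sensation stay as tolerability measures on that basis. Leave resolution to the efficacy criterion in Section 7.1.
4. Express the vision limit consistently with 0.10 logMAR per line, and count worsening only.
5. Reconcile the corneal rows: the remission table accepts an affected area below 95%, while the safety table gives 95% with no comparison sign, possibly lost in conversion. The verdict does not rest on this.

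**Cost.** One sentence and the value column of the safety table change. The schedule in Section 8 (Table 2) already collects symptoms, vision, anterior and posterior examination and adverse events at unscheduled and discontinuation visits, so no new visits, data or patients are needed. Changing a safety criterion may count as a substantial amendment under Section 29.2, with the ethics and authority submissions that this entails.
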